7	SAFETY MANAGEMENT	9
7.1	CLINICAL ADVERSE EVENTS	9
7.2	ADVERSE EVENT REPORTING	9
8	STUDY ADMINISTRATION	9
8.1	TREATMENT ASSIGNMENT METHODS	9
8.1.1	Randomization	9
8.2	DATA COLLECTION AND MANAGEMENT	10
8.3	CONFIDENTIALITY	10
8.4	REGULATORY AND ETHICAL CONSIDERATIONS	10
8.4.1	Risk Assessment	10
8.4.2	Potential Benefits of Trial Participation	11
8.4.3	Risk-Benefit Assessment	11
8.5	RECRUITMENT STRATEGY	11
8.6	INFORMED CONSENT/ASSENT AND HIPAA AUTHORIZATION	12
8.6.1	Waiver of Consent	12
8.6.2	Waiver of Assent	122
8.6.3	Waiver of HIPAA Authorization	122
8.7	PAYMENT TO SUBJECTS/FAMILIES	12
8.7.1	Gifts	122
9	PUBLICATION	12
10	REFERENCES	13
	APPENDIX I	14
	APPENDIX II	15

ABBREVIATIONS AND DEFINITIONS OF TERMS

TI	Tracheal Intubation
NICUs	Neonatal Intensive Care Units
VL	Video Laryngoscopy
NEAR4KIDS	National Emergency Airway Registry for Kids
TIAE	Tracheal Intubation Associated Event
DCC	Data Coordinating Center
NIH	National Institute of Health
AE	Adverse Event
SAE	Severe Adverse Event

ABSTRACT

Context: (Background)

Tracheal intubation (TI) is the most common life-saving intervention for resuscitation and stabilization of critically ill neonates in Neonatal Intensive Care Units (NICUs).

Recently, video laryngoscopy (VL) has become available in neonatal clinical practice to allow trainees and frontline providers to perform standard direct airway visualization (i.e., traditional laryngoscopy) while the supervisor can simultaneously view a real-time video displaying what the laryngoscopist is seeing. However, VL associated coaching during TI has not been rigorously evaluated.

Objectives: (primary and important secondary objectives)

To determine if a video laryngoscope assisted real-time coaching intervention can reduce adverse TI associated events and desaturation across academic NICUs.

Study Design:

A quasi-experimental before-after design with educational quality improvement interventions at multiple NICUs with randomly staggered timing for educational intervention (as known as stepped-wedge design) based on the NICU characteristics.

Setting/Participants:

Neonatal ICUs in academic centers across the United States and Canada.

Approximately 10 NICU sites with up to 24 faculty at each site (up to 240 faculty, senior nurse practitioners, physician assistants and respiratory therapists with at least 5 years of clinical neonatology experience).

Approximately 1800 trainees and frontline providers who are qualified to perform tracheal intubation under attendings supervision.

Study Interventions and Measures:

Study intervention is a VL coaching training for site neonatology attendings, nurse practitioners, physician assistants, and respiratory therapists. Each site leader/key educator will be trained remotely by expert co-investigators. Site leaders and key educators will train their attendings, NPs, PAs, and RTs. The quality of VL coaching skills will be verified by randomly auditing 20% of attending providers, NPs, PAs, and RTs at each site for their skill assessment by remote simulation during the transition/post-intervention phase. The timing of VL coaching implementation will be randomly staggered between 6-12 months.

The primary endpoint is the occurrence of adverse tracheal intubation associated events in primary intubations in NICUs. These data points are recorded through the existing observational registry study: NEAR4KIDS CHOP IRB number 09-007253.

The secondary endpoint is the successful completion of all faculty staff training at participating sites, and their performance in the follow up skill evaluation using audio-recording as well as the change in the occurrence of severe oxygen desaturation (absolute oxygen saturation drop $>20\%$ from baseline) across 10 academic NICUs

PROTOCOL SYNOPSIS

Study Title	Improving safety and quality of tracheal intubations in neonatal ICUs
Funder	National Institutes of Health (NIH)
Clinical Phase	Not applicable
Study Rationale	
Tracheal intubation (TI) is the most common life-saving intervention for resuscitation and stabilization of critically ill neonates in Neonatal Intensive Care Units (NICUs). More than 400,000 neonates are admitted to NICUs in the US annually, and 10%-15% of these infants (>40,000) require TI to sustain life. TI procedures are high risk. Adverse TI associated events are frequent (20%) and severe desaturation during TI (>20% absolute decrease in oxygen saturation) occurs in >50%. Neonatal TIs have unique risks related to difficult airway anatomy (e.g., anterior larynx) and physiology (e.g. limited pulmonary oxygen reserve) requiring prompt procedural success. Provider technical skills, suboptimal TI approach such as underuse of neuromuscular blockade, and communication errors contribute to neonatal TI risks.
 
Previous TI studies indicate that training level and multiple attempts are associated with adverse TI associated events and severe desaturation. Video laryngoscopy (VL) is now available in neonatal practice, but standard direct laryngoscopy technique for TI remains a core clinical skill. Newer VL technology allows trainees and frontline providers to perform standard traditional laryngoscopy while their supervisor can simultaneously view a real time video display of what the trainee/laryngoscopist is actually seeing. This technology enables expert “coaching” by a supervisor for the hazardous TI procedure.

Study Objective(s)	
Primary
 
 To determine if a novel video laryngoscope assisted real-time coaching intervention can reduce adverse TI associated events across approximately 10 academic NICUs 
Secondary
 
 To determine if a novel video laryngoscope assisted real-time coaching intervention can reduce severe oxygen desaturation (absolute oxygen saturation drop >20% from baseline) across 10 academic NICUs To determine duration till completion of faculty training and evaluate faculty performance during transition/post-intervention phase

Study Design	A quasi-experimental before-after design with educational quality improvement interventions.
Subject Population key criteria for Inclusion and Exclusion:	
Inclusion Criteria
 
 • Subjects age 22-above • VL coach: Neonatology attending physician position at each neonatal ICU, or Senior trainees who are anticipated to graduate within next 6 months to become neonatology attending physicians, nurse practitioners with over 5 years of clinical experience, physician assistants and respiratory therapists with over 5 years of clinical neonatology experience. • VL coach receivers: Trainees (medical students, residents, fellows except those graduating within next 6 months) and frontline providers (nurse practitioners, hospitalists, physician assistants, respiratory therapists, others who perform tracheal intubations under attending physicians' supervision): 
Exclusion Criteria
 
 • None
Number Of Subjects	Total Number of Subjects: 240 faculty across approximately 10 NICUs, Total Number of Sites: 10 sites
Study Duration	Each subject's participation will last for 2 years The entire study is expected to last 2 years
Study Phases Screening Study Treatment Follow-Up	
This study have 3 phases.
 
Pre-intervention phase: evaluation of tracheal intubation with or without video laryngoscopy use as a baseline
 
Transition phase: From initiation of remote site leader training ('train the trainer' session) until the pre-defined site-level uptake (>70% VL use for trainee/frontline TIs per month).
 
Post-intervention phase: We will continue to capture all TIs after VL use meets criteria >70%.

Efficacy Evaluations	Occurrence of adverse TIAEs
Safety Evaluations	The occurrence of adverse TIAEs, desaturation, and multiple attempts
Statistical And Analytic Plan	
For primary and secondary endpoint (adverse TIAEs, severe desaturation rate), the event rates will be compared between pre-intervention phase and post-intervention phase. We plan to censor the transition phase for the primary analysis.
 
For secondary endpoint (duration till completion of faculty training and faculty performance during transition/post-intervention phase),

a summary statistics will be developed and will be compared against effect size (decrease in adverse TIAE rates) and VL use.

**DATA AND SAFETY
MONITORING PLAN**

The plan for tracheal intubation data accuracy and safety is under NEAR4KIDS protocol CHOP IRB number 09-007253. Regarding the neonatology faculty training data, data manager will be in charge for the accuracy, quality and safety of the data. Data will be kept in REDCap database with only limited access to PI, Data Coordinator and Data manager.

TABLE 1: SCHEDULE OF STUDY PROCEDURES

Study Phase	Screening/ Training	Follow up
Visit Number	1	2
Study Days		
Informed Consent	X	
Review Inclusion/Exclusion Criteria	X	
Demographics	X	X
Training by site leader	X	
Remote simulation for skill assessment		

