3.1.3 Transition Phase

Transition phase: From initiation of remote site leader training ('train the trainer' session) between the overall PI and site leaders, until the pre-defined site-level uptake (>70% VL use for trainee/frontline TIs per month). The tracheal intubation data during this period will be censored for a primary analysis, and will be used for secondary analyses.

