3.3 Study Duration, Enrollment and Number of Sites

3.3.1 Duration of Study Participation

The study duration per subject (neonatologist attendings, NPs, PAs and RTs) will be up to 18 months, the longest. After their initial video coaching training, 20% of the attending physicians, NPs, PAs, and RTs will be randomly chosen to participate in a follow up skill evaluation with a remote simulation.

The study duration per subject (nurse practitioners, hospitalists, physician assistants, respiratory therapists, others who perform tracheal intubations under attending physicians' supervision) will be up to 24 months, the longest. They may be approached for study consents before their NICU rotation.

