6.3 Sample Size and Power

For the primary outcome of the occurrence of TIAEs, we plan to obtain a data from ongoing observational study database (NEAR4NEOS) for a total sample size of 2,900 tracheal intubations: 145 tracheal intubations during pre-intervention and 145 tracheal intubations during post-intervention phase per site from 10 sites over 2 years (a total of 1450 tracheal intubations before the intervention and 1450 intubations after the intervention). We anticipate a decrease of adverse TIAEs from 20% to 16 % (absolute risk reduction of 4%, relative risk reduction of 20%). Note this estimate is adjusted to account for site-level clustering. Also the number of tracheal intubations will be variant across the sites. Since this study is an educational intervention and pre-post design, we will include all tracheal intubation data during the 2 year study period.

6.4 Interim Analysis.

No stopping rule is applied. Each site performance in tracheal intubation safety and video laryngoscopy use will be reported in aggregate as benchmark data as a part of quality improvement activity during the study period.

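### With coaching starts in months 6-12 and the transition censored, little or no calendar time may hold both pre- and post-phase sites, so the primary contrast is largely before-after

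*Combined protocol and SAP*

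**What the plan says.** - **Design.** The Abstract (Study Design) describes a quasi-experimental before-after study with "randomly staggered timing for educational intervention (as known as stepped-wedge design) based on the NICU characteristics". Under Study Interventions and Measures it adds: "The timing of VL coaching implementation will be randomly staggered between 6-12 months".
- **Length.** Protocol Synopsis, Study Duration: "The entire study is expected to last 2 years". Section 3.3.1 says participation of the coaches "will be up to 18 months, the longest".
- **Transition.** Under section 3.1.3 it runs from remote training of the site leader until video laryngoscope use passes 70% of trainee and frontline intubations in a month. No expected, minimum or maximum length is given. "The tracheal intubation data during this period will be censored for a primary analysis, and will be used for secondary analyses".
- **Comparison.** The Synopsis (Statistical And Analytic Plan) and section 6.2.2 compare pre- and post-phase event rates. No model or calendar-time term is named.
- **Size.** Section 6.3 plans "145 tracheal intubations during pre-intervention and 145 tracheal intubations during post-intervention phase per site from 10 sites over 2 years", for a fall in TIAEs from 20% to 16%.

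**The concern.** A random stagger is useful because sites not yet trained act as concurrent controls for sites already trained. That needs calendar months in which some sites are pre-phase and others are post-phase. Here the stagger window is short, and each site's first months after its start, when those controls would exist, are the ones removed.

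The plan itself makes a time trend plausible. Section 1.4 says video laryngoscopy is spreading in pediatric practice, and section 8.4.2 says it is becoming standard in many institutions. If the phases hardly overlap, a fall in TIAEs from such changes cannot be told apart from a coaching effect. Adding a time term to the model would expose this weakness but not cure it.

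In addition, only the start is randomised. The post phase begins when a site reaches the uptake threshold, so the censored contrast does not follow the randomisation.

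**Working it through.** **1. The plan's own sample size.** Alpha and power are not stated; I assume two-sided 5% and 80%. With a mean rate of 0.18:

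n = [1.96·√(2·0.18·0.82) + 0.842·√(0.20·0.80 + 0.16·0.84)]² / 0.04² = (1.065 + 0.457)² / 0.0016 ≈ 1,447 per phase.

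The stated 1,450 reproduces. It is the size for a comparison of two independent proportions with no time term.

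**2. Ceiling on overlap.** Read the stagger as starts after months 6 to 12 of 24. The 18 months for coaches in section 3.3.1 fits this, since 24 − 6 = 18. No site is pre-phase after month 12. With a transition of T months, none is post-phase before month 7 + T. Months holding both phases = 6 − T, and 0 once T reaches 6.

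**3. Transition implied by 145/145.** The mean start is (6 + 12)/2 = 9 months. At constant volume that is 145/9 ≈ 16.1 intubations per site-month, so 145 post-phase intubations also take 9 months. This leaves 24 − 9 − 9 = 6 months. If 145/145 is applied site by site, a start after month s gives a transition of 24 − 2s months (12 for s = 6, 0 for s = 12). The post phase then begins after month 24 − s, never before month 12, and overlap is again zero.

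**4. Precision.** Assumptions: 10 equal sites, starts spread evenly over months 6-12, 16 intubations per site-month, event rate 18%, ICC 0.02. The model is generalised least squares on site-month means with a random site intercept, fixed month effects and transition cells removed. Power for 4 points is Φ(4/SE − 1.96).

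| Transition (months) | Overlap months | SE (points) | Power |
|---|---|---|---|
| 0 | 6 | 3.1 | 25% |
| 1 | 5 | 3.6 | 19% |
| 3 | 3 | 5.7 | 10% |
| 4 | 2 | 8.1 | 7% |
| 5 | 1 | 13.8 | 5% |
| 6 | 0 | not estimable | – |

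At a 6-month transition, a linear trend in place of month effects gives SE 4.1 and power 16%. With no time term, power is 79%.

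**5. Sensitivity.**
- ICC from 0.01 to 0.05 changes almost nothing.
- Placement of starts matters. With half the sites at month 6 and half at month 12 (site fixed effects), transitions of 1 to 5 months give SE 3.1 to 6.3 and power 25% to 9%.
- If transitions vary by site around a mean of 6 months (4-8, 2-10 or 1-11), mean overlap is 1.0, 2.3 or 2.9 months and median power about 5% to 9%.
- If starts spread over 12 months, a 6-month transition leaves 6 overlap months, SE 4.3 and power 15%.

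**6. Keeping transition data.** Counting each site as exposed from its start restores the zero-transition layout, so the SE is 3.1 whatever the transition length.

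**The case against.** A reader might infer that the design cannot separate coaching from time under any model. The documents do not support that.

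- **No transition length is stated.** It ends on an uptake trigger and could be short. The 6 months comes from treating 145 per site as an accrual forecast, but step 1 shows that it matches a rounded power target. The plan also says "Also the number of tracheal intubations will be variant across the sites".
- **The calendar is not settled.** Section 2.1 refers to 2 years before and after the intervention. Section 3.1.4 allows post-phase capture for up to 2 years, and section 3.3.2 counts 2 years per site. The Synopsis gives each subject 2 years, against 18 months for coaches in section 3.3.1. A longer post phase adds no overlap, because it adds no pre-phase months, but it does remove the basis for deriving 6 months.
- **The stagger wording is ambiguous.** It could mean start months, total spread or step spacing.
- **Non-estimability is a special case.** It needs zero overlap and categorical month effects. A linear trend remains estimable, though only by relying on a trend shape that the data cannot test across the gap.
- **The plan is open about its design.** It calls itself quasi-experimental before-after, and it already assigns transition data to secondary analyses.

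All of this stands, and it makes the zero-overlap statement conditional. It does not rescue precision: no scenario in steps 4 and 5 gives a month-adjusted analysis more than about 25% power.

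**Conclusion.** The concern holds conditionally and should be fixed. With starts in months 6-12 of a common 24-month calendar, overlap is at most six months and shrinks by about one month per month of uniform transition. It is zero at the roughly 6 months implied if 145/145 is read as accrual. At 1 to 5 months, month-adjusted SEs are about 3.6 to 13.8 points against a 4-point target, on the assumptions in step 4. These figures are a guide to scale, since site volumes, ICC and the step schedule are not given.

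The censored primary comparison is therefore largely an uncontrolled before-after contrast, and 1,450 per phase supports only that. What does not follow is that the time-adjusted effect is certain to be inestimable.

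**What to change.** 1. **Add an analysis.** Beside the censored comparison, pre-specify one with site and calendar-time effects that counts each site as exposed from its randomised training start and keeps transition intubations. This changes wording only, because the registry already captures the data. The cost is some dilution of the effect by the learning period.
2. **State its limits.** Say that this analysis has about 25% power for 4 points (SE 3.1), that 1,450 per phase supports only the before-after comparison, and that causal claims will be limited to match.
3. **State the step schedule and the expected transition length.**
4. **Reconcile the text.** The Synopsis and sections 2.1, 3.1.3, 3.1.4, 3.3.2 and 6.3 disagree on study length and on which data are included. Section 6.3 includes all intubations in the 2 years, while the transition is censored elsewhere.

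A wider spread of starts is an option to weigh, not a required change. Starts over months 3-18 with censoring give SE 2.7 for a 3-month transition and 3.5 for a 6-month one. In the 6-month case, however, the last site has no post phase (18 + 6 = 24), and post-phase intubations fall to about 1,200 (75 site-months × 16) against 1,450 planned.

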1 BACKGROUND INFORMATION AND RATIONALE

1.1 Introduction

Tracheal intubation (TI) is the most common life-saving intervention for resuscitation and stabilization of critically ill neonates in Neonatal Intensive Care Units (NICUs). More than 400,000 neonates are admitted to NICUs in the US annually, and 10%-15% of these infants (>40,000) require TI to sustain life. TI procedures are high risk. Adverse TI associated events are frequent (20%) and severe desaturation during TI (>20% absolute decrease in oxygen saturation) occurs in >50%. Neonatal TIs have unique risks related to difficult airway anatomy (e.g., anterior larynx) and physiology (e.g. limited pulmonary oxygen reserve) requiring prompt procedural success. Provider technical skills, suboptimal TI approach such as underuse of neuromuscular blockade, and communication errors contribute to neonatal TI risks.

Previous TI studies indicate that training level and multiple attempts are associated with adverse TI associated events and severe desaturation. Video laryngoscopy (VL) is now available in neonatal practice, but standard direct laryngoscopy technique for TI remains a core clinical skill. Newer VL technology allows trainees and frontline providers to perform standard traditional laryngoscopy while their supervisor can simultaneously view a real time video display of what the trainee/laryngoscopist is actually seeing. This technology enables expert “coaching” by a supervisor for the hazardous TI procedure.

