5 STUDY EVALUATIONS AND MEASUREMENTS

5.1 Screening and Monitoring Evaluations and Measurements

5.1.1 Demographic Data Collection

Brief demographic data of each neonatology attending, NP, PA, and RT participant (subject) will be obtained. These data points are listed below:

- Age
 - Gender
 - Years of experience as neonatology attending
 - Years of experience in Neonatology as a Nurse Practitioner
 - Years of experience in Neonatology as a Respiratory Therapist
 - Years of experience in Neonatology as a PA
 - Year of neonatology fellowship completion
 - Year of completed NP training
 - Year of completed RT training
 - Year of completed PA training
 - Experience in video laryngoscopy use
-

- Months of experience in video laryngoscopy use

Brief demographic data of each neonatology trainees and frontline providers will be obtained. These data points are listed below.

- Age
- Gender
- Training level
- Training experience (type and length of residency training, type and length of fellowship training)
- Training experience before joining post-graduate education in the United States
- Experience in laryngoscopy use (number of previous intubation in patients)
- Confidence in laryngoscopy use (Likert scale)

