6.2.2 Efficacy Analysis

The primary efficacy endpoint will be the change in the occurrence of adverse tracheal intubation associated events among all primary tracheal intubations in neonatal ICUs between pre-intervention phase and post-intervention phase.

Secondary endpoints will include the change in the occurrence of severe desaturation (absolute oxygen saturation drop >20% from baseline) between pre-intervention phase and post-intervention phase.

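### The pre/post rate comparison names no model and no adjustment for operator training level, site or calendar time, so a shift in operator mix would be read as intervention effect

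*Combined protocol and SAP*

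**What the plan says.** The Synopsis (Statistical and Analytic Plan) says that, for adverse TIAEs and severe desaturation, "the event rates will be compared between pre-intervention phase and post-intervention phase". It adds: "We plan to censor the transition phase for the primary analysis". Section 6.2.2 reads: "The primary efficacy endpoint will be the change in the occurrence of adverse tracheal intubation associated events among all primary tracheal intubations", pre versus post. It then gives the desaturation endpoint in the same form. Neither place names a test, model, covariate, site term or calendar-time term, and Section 6.1 adds none. Section 6.3 says the sample-size estimate allows for clustering by site, but that remark concerns the estimate and not the analysis.

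On operators, Section 1.1 and the Synopsis rationale both state: "Previous TI studies indicate that training level and multiple attempts are associated with adverse TI associated events and severe desaturation". Section 5.1.1 collects training level for trainees and frontline providers, and also "Experience in laryngoscopy use (number of previous intubation in patients". Section 5.2.1 plans to record provider IDs against intubations and to merge provider demographics on those IDs.

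On timing, the Abstract says: "The timing of VL coaching implementation will be randomly staggered between 6-12 months". On saturation, the only reference is the endpoint definition, "absolute oxygen saturation drop >20% from baseline"; no data field for the baseline value is listed.

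**The concern.** Within each site the two phases are ordered in time, and no intubation is randomised to a phase. The comparison is therefore fair only if the operators and infants are similar in both phases, or if the analysis allows for differences.

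The operators are a changing group. About 1800 trainees and frontline providers are expected, and trainees within 6 months of graduation count as coaches instead of coach receivers (Section 3.4.1). If the share of intubations by less experienced operators falls between phases, the event rate falls without any effect of coaching. If that share rises, a real benefit is partly hidden.

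The randomly staggered start could separate the intervention from time trends, but only if the analysis uses calendar time. A comparison of pooled phase rates does not.

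**Working it through.** **1. The plan's own figure.** Inputs from Section 6.3: 20% before, 16% after, and 145 × 10 sites = 1450 intubations per phase. The documents state neither alpha nor power, so two-sided 5% and 80% are assumed. Two-proportion formula with pooled variance:

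n = [1.96 × √(2 × 0.18 × 0.82) + 0.842 × √(0.20 × 0.80 + 0.16 × 0.84)]² / 0.04² = 1447 per phase.

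This matches the stated 1450, at which power is 80.1%. The sample size therefore fits a simple comparison of two rates with no covariates. That is consistent with the Synopsis sentence but does not prove what the sponsor intends.

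**2. Is the operator covariate available?**
- Training level is collected (5.1.1), but only after consent (4.1). Intubation data are collected whatever the provider's status (4.3), so some intubations may lack it.
- One sentence of 5.2.1 has the attending and the trainee or frontline provider recorded for each intubation. The two added fields, however, are for the coach and the provider who received coaching.
- Section 3.1.2 defines the pre-intervention phase as without coaching language. Whether linkage is complete in that phase is not settled.
- The uptake rule of more than 70% (3.1.3) needs intubations classed as trainee/frontline or other. Some operator category must therefore exist, though the rule does not require seniority.

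**3. Size, simple form.** Bias = risk gap between operator groups × change in their share. Neither factor is in the documents; both are assumed.
- 10-point gap, 10-point shift: 0.10 × 0.10 = 1.0 point, and 1.0 / 4 = 25% of the target.
- 5-point gap, 10-point shift: 0.5 point, 13% of the target.
- 15-point gap, 20-point shift: 3.0 points, 75% of the target.

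**4. Size, with the chance of a false benefit.** Assume no intervention effect, 20% overall risk before, half of pre-phase intubations in the higher-risk group, and a risk ratio RR between groups. Lower-group risk = 0.20 / (0.5 × RR + 0.5). Apparent reduction = (higher risk − lower risk) × fall in the higher-risk share. The chance of a significant false benefit uses 1450 independent intubations per phase; its nominal value is 2.5%.

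| RR | Risks, lower / higher | 5-point fall | 10-point fall | 20-point fall |
|---|---|---|---|---|
| 1.5 | 16.0% / 24.0% | 0.40 pt, 4.6% | 0.80 pt, 7.8% | 1.60 pt, 19.3% |
| 2.0 | 13.3% / 26.7% | 0.67 pt, 6.6% | 1.33 pt, 14.7% | 2.67 pt, 45.4% |
| 2.5 | 11.4% / 28.6% | 0.86 pt, 8.4% | 1.71 pt, 21.6% | 3.43 pt, 66.7% |

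To produce the full 4 points from mix alone, the share would have to fall by 0.04 / gap: 50, 30 and 23 points for RR 1.5, 2.0 and 2.5. A rise in the higher-risk share gives a bias of the same size in the opposite direction.

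**The case against.** The strongest reply is that silence is not a choice. The documents never call the comparison raw or unadjusted; they name no method. The planned merge of provider demographics with intubation records suggests some use of those data is intended. This stands as far as wording goes: a reader might infer that the sponsor has decided against adjustment, and the text does not support that. What is documented is a rate comparison with no model and no covariates. Followed as written, it leaves operator mix confounded with phase.

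Four further inferences are tempting and not supported:
- **Baseline saturation is on file.** It is only implied by the endpoint definition. The registry's field list belongs to a separate protocol, and the registry might hold only a yes/no flag.
- **The pre phase lasts 6 to 12 months and so misses part of an academic year.** The Abstract says implementation is staggered over that range, which does not fix the length of the pre phase. Staggered starts may also offset seasonal effects across sites.
- **The mix will shift.** Nothing shows a shift or its direction.
- **Adjustment will gain precision.** In a logistic model it need not reduce the standard error of the log odds ratio, and a calendar-time term is correlated with phase and may widen the interval.

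A last objection concerns the estimand. Coaching may lead supervisors to let more junior operators intubate. Operator level would then be partly a result of the intervention, and adjusting for it would no longer estimate the programme's total effect. This stands, and it is why both contrasts should be reported.

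**Conclusion.** The concern holds in a limited form. The primary and desaturation comparisons are between non-randomised, time-ordered phases, with no model and no prespecified allowance for site, calendar time or a risk factor that the protocol itself names, collects and plans to link. A change in operator mix would pass straight into the estimated effect, in either direction.

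The size is unknown. The 1-point example and the table rest wholly on assumed gaps, shares and shifts, and the false-benefit figures also treat intubations as independent. They show that moderate shifts would matter against a 4-point target, and also that mix alone would need a large shift to produce all of it. They are not an estimate of bias in this trial. The case for training level is firm; the case for baseline saturation depends on a field not yet confirmed. The covariates should be fixed in advance, because choosing them after seeing a shift would be data-driven.

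**What to change.** In Section 6.2.2, replace the bare rate comparison with an intubation-level model for the pre/post contrast, keeping the endpoint definitions and the exclusion of the transition phase:

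- Account for clustering by site, and name the link function and the clustering method.
- Include calendar time. The staggered starts make it separable from phase.
- Include operator training category as a prespecified covariate, with one definition available in both phases. If linkage to the 5.1.1 data is incomplete before the intervention, use the registry operator category throughout; mixing sources by phase could itself add bias. State how missing categories are handled.
- Report the same contrast without the operator term alongside, because coaching could change who intubates. Give the observed rates descriptively.
- For severe desaturation, add pre-laryngoscopy saturation as a continuous covariate only if the registry is confirmed to hold the value.

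The cost is SAP wording, a check of which registry fields exist in the pre-intervention phase, and modest analysis work. Some operator data will probably be missing, and the calendar-time term may widen the confidence interval.
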